## 13.2.4 Retention of records

The Principal Investigator of The Case Comprehensive Cancer Center supervises the retention of all documentation of adverse events, records of study drug receipt and dispensation, and all IRB correspondence for as long as needed to comply with national and international regulations. No records will be destroyed until the Principal Investigator confirms destruction is permitted.

## 13.2.5 Audits and inspections

Authorized representatives of the sponsor, a regulatory authority, an Independent Ethics Committee (IEC) or an Institutional Review Board (IRB) may visit the Center to perform audits or inspections, including source data verification. The purpose of an audit or inspection is to systematically and independently examine all study-related activities and documents to determine whether these activities were conducted, and data were recorded, analysed, and accurately reported according to the protocol, Good Clinical Practice (GCP), guidelines of the International Conference on Harmonization (ICH), and any applicable regulatory requirements.

*13.2.6 Data Safety and Monitoring Plan* This protocol will adhere to the policies of the Case Comprehensive Cancer Center Data and

Safety Monitoring Plan in accordance with NCI regulations.

#### 14.0 STATISTICAL CONSIDERATIONS

#### 14.1 Study Design/Endpoints

The primary endpoint of this trial will be the overall response rate (biologic response rate+CR + PR; CR/PR are based on NCI-WG (for CLL) and Cheson criteria (for SLL). The point estimate of the overall response rate and biologic response rate along with 95% confidence intervals will be calculated using binomial distribution theory. The secondary efficacy variables of: Time to first cytotoxic treatment (TFCT), progression free survival (PFS) and overall survival (OS) will be estimated using Kaplan-Meier method and displayed graphically. Duration of response will also be calculated as a secondary variable of efficacy.

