#### 2.1 **Primary Objective**

To determine the overall response rate (ORR) based on NCI-WG criteria in CLL or the Cheson criteria in SLL. Will also examine biologic response rate (78); defined as at least 20% reduction of absolute lymphocyte count (ALC) that is sustained over 2 months or  $a \ge 30\%$  reduction in palpable lymphadenopathy using this regimen.

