#### 12.4 Biologic response criteria CLL and SLL (78)

Given the favorable toxicity profile of curcumin and vitamin D3 in healthy adults and the intention to evaluate the efficacy of both agent to delay or prevent PD in patients with CLL/SLL, we also evaluated an additional response category termed "biologic response" among patients who did not meet standard NCI-WG criteria for CR and PR. The criteria for a biologic response were prospectively defined in a recent study of Polyphenon E, after discussion and approval of the NCI. Polyphenon E, very much like curcumin and vitamin D3, is the most active ingredient in green tea extract and it works through unique, noncytotoxic mechanisms. Biologic response was defined as a reduction in the absolute lymphocyte count (ALC) of > 20% from the pretreatment level that was sustained for at least 2 months or  $a \ge 30\%$  reduction in all palpable lymphadenopathy (78).

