#### 12.5 Duration of Response

#### **Duration of overall response:**

The duration of overall response is measured from the time measurement criteria are met for CR or PR (whichever is first recorded) until the first date that recurrent or progressive disease is objectively documented (taking as reference for progressive disease the smallest measurements recorded since the treatment started).

The duration of overall CR is measured from the time measurement criteria are first met for CR until the first date that progressive disease is objectively documented.

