#### 14.2 Sample Size/Accrual Rate

The sample size is calculated for a single arm, Simon optimal 2-stagephase II deign. The design to test the null hypothesis that  $P \le 0.1$  versus the alternative that  $P \ge 0.3$  has a sample size of 29 and a probability of early termination of 0.74 under the null. The power is 0.8 with statistical significance declared at an alpha level of 0.05. An accrual goal of 35 patients will be enrolled in this study to allow 20% ineligibility or drop outs. According to the Simon 2-stage method, 10 patients will be accrued initially during stage I. If there is evidence of clinical benefit, the remaining 25 patients will be enrolled during stage II. For the purpose of stopping the trial for futility, clinical benefit is defined as biologic response or better (please refer to section 12.4 for the definition of biologic response).

In the planned Simon 2-Stage analysis, 10 patients will be enrolled in stage I. An interim analysis will be performed after the 10th patient completes the induction therapy period. If 1 or fewer patients exhibit clinical benefit (biologic response or better), the trial will be stopped. If 2 or more patients demonstrate clinical benefit, the study will proceed to stage II and an additional 19 patients will be enrolled and treated. If the trial goes on to the second stage, a total of 29 eligible patients will be studied. If the total number responding is less than or equal to 5, the drug combination is considered not worth further exploration. The entire study group of 35 patients will be evaluated in the final analysis.

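### Overall response has two meanings in the plan, and the 29-patient decision rule sits beside a 35-patient analysis; the Simon design holds for a 29-patient composite, but a positive result should not be called an ORR

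*Combined protocol and SAP*

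**What the plan says.** **The endpoint label.** The primary objective in 2.1 reads "To determine the overall response rate (ORR) based on NCI-WG criteria in CLL" (Cheson criteria for SLL) and then adds biologic response as a further rate to examine. Section 12.4 presents biologic response as an extra category for patients who fall short of CR and PR. Section 12.5 follows the 2.1 usage: "The duration of overall response is measured from the time measurement criteria are met for CR or PR". Section 14.1 does not: "The primary endpoint of this trial will be the overall response rate (biologic response rate+CR + PR". Section 14.4.2 assigns each patient a single category (CR, PR, stable, progressive, three kinds of early death, unknown), and biologic response is not among them.

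**The decision rule.** Section 14.2 sets a Simon optimal two-stage design, 10% against 30%, with 10 patients in stage I and 29 in total. For the interim: "For the purpose of stopping the trial for futility, clinical benefit is defined as biologic response or better". For the end of the trial: "If the total number responding is less than or equal to 5, the drug combination is considered not worth further exploration". Responding is not defined again for that second count.

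**The analysis set.** Section 3.2 enrols up to 35 to obtain 29 evaluable patients. Section 3.3 allows replacement of those not evaluable. Section 14.2 speaks of 29 eligible patients, then says all 35 enter the final analysis. Section 14.4.1 plans 35 evaluable. Section 14.4.2 requires two cycles for evaluability, then places all eligible patients in the main response analysis (with a possible exception for those never treated) and counts categories 4 to 9 as failures.

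**The rates.** Section 1.4 supports 30% by the historical ORR to chlorambucil. No source is given for 10%, and no expected rate is given for biologic response.

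**Biologic response.** Section 2.1 has "at least 20% reduction of absolute lymphocyte count (ALC) that is sustained over 2 months" or a 30% reduction in palpable nodes. Section 12.4 has "a reduction in the absolute lymphocyte count (ALC) of > 20% from the pretreatment level that was sustained for at least 2 months" or a 30% "reduction in all palpable lymphadenopathy".

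**The concern.** The same words name two different endpoints, and the difference is large in clinical terms: a lymphocyte fall of about 20% counts in one and not in the other. Section 14.1 would report a composite carried entirely by biologic responses as an overall response rate, and readers would set it beside a 30% figure that comes from conventional chlorambucil responses. In that case 12.5 would supply no patient with a duration of response. The single-category list in 14.4.2 cannot on its own produce the 14.1 endpoint, since a biologic responder would most likely be filed as stable disease.

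The second issue is the denominator. A Simon cut-off is valid for the number of patients it was derived for. With 29 and 35 both presented as the final set, and with both an evaluable and an all-eligible population in 14.4.2, the analyst has to choose, and the stated 0.05 depends on that choice.

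**Working it through.** **Inputs.** All from 14.2: p0 = 0.10, p1 = 0.30, n1 = 10, stop if 1 or fewer, N = 29, not promising if 5 or fewer. Sidedness of alpha is not stated; a Simon design is one-sided.

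**Formulas.** Early termination = P(X1 ≤ 1), with X1 ~ Bin(10, p). P(positive) = Σ over x from 2 to 10 of P(X1 = x) × P(Bin(N − 10, p) ≥ 6 − x).

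**Step 1: reproduce the plan (composite at both stages, N = 29).**
- Early termination at 10%: 0.9^10 + 10 × 0.1 × 0.9^9 = 0.3487 + 0.3874 = 0.7361 (stated 0.74).
- Type I error, terms for x = 2, 3, 4, 5 and 6 or more: 0.1937 × 0.1150 + 0.0574 × 0.2946 + 0.0112 × 0.5797 + 0.0015 × 0.8649 + 0.0001 = 0.0471 (stated 0.05; the test is discrete).
- Power at 30%, same sum: 0.8051 (stated 0.8).

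A search over designs with N below 40 also returns 10/29 with cut-offs 1 and 5 as the optimal design. The calculation in 14.2 is correct.

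**Step 2: what a positive result can contain.** The smallest positive count is 6/29 = 20.7%, exact 95% CI 8.0% to 39.7%. It is compatible with 0/29 CR+PR, exact 95% CI 0 to 1 − 0.025^(1/29) = 11.9%. This is a possible outcome, not a forecast.

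**Step 3: cut-off of 5 on a larger set.** Same formula, N changed, every patient given a 10% (or 30%) chance:

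| N | Type I error | Power |
|---|---|---|
| 29 | 0.047 | 0.805 |
| 30 | 0.053 | 0.815 |
| 31 | 0.058 | 0.822 |
| 32 | 0.064 | 0.828 |
| 33 | 0.070 | 0.833 |
| 34 | 0.076 | 0.837 |
| 35 | 0.082 | 0.840 |

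**Step 4: the same 35 with losses counted as failures.** Assume that only 29 of 35 can respond and the rest count as failures, spread evenly over both stages. The per-patient rate becomes 0.10 × 29/35 = 0.0829 under the null and 0.30 × 29/35 = 0.2486 under the alternative. Type I error is then about 0.040 and power about 0.72 (0.715).

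**Step 5: the rates.** The 30% in 1.4 is a conventional ORR, and the tested quantity in 14.1 adds biologic response. No arithmetic links the two, because the documents give no biologic response rate.

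**The case against.** The strongest reply is that the plan can be read coherently. Section 14.1 names the composite as primary, 14.2 tests one Simon design on it, and the stage I count already uses biologic response or better, so the final count should mean the same. That stands. A reader might instead infer that the final count is CR+PR only. The type I error would then be about 0.057 to 0.061, assuming CR+PR of 10% and a composite rate of 20% to 30%. The documents do not support that reading over the composite, and those rates are not in the plan.

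A reader might also infer that the plan applies the cut-off of 5 to 35 patients and so runs at 0.082. The text does not say so: 14.2 attaches the cut-off to 29 eligible patients, and 3.2 explains the 35 as an allowance for losses. The 0.082 also needs all 35 to have a full 10% chance, and Step 4 shows that the error can fall below 0.05. What remains is that 14.2 and 14.4.2 leave the decision set open, and some permitted choices break the stated level.

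It could be said that no interval is planned for CR+PR. That is only one reading. Section 14.1 lists intervals for the overall and the biologic response rates side by side, and the first could mean CR+PR as in 2.1.

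Two further replies have partial force. Section 14 makes no formal chlorambucil comparison, and 1.4 points to section 12, which includes the biologic criteria; but the stated support for 30% is still a conventional response rate. The two wordings of the lymphocyte threshold differ only at exactly 20%, and 14.2 already refers to 12.4; the presence or absence of the word all for the nodes matters somewhat more. Both are minor.

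**Conclusion.** The point holds as an inconsistency of endpoint name, benchmark and analysis set. It is not a failure of the design. On the natural reading (composite at both stages, 29 patients) the screening verdict stands, with type I error 0.047 and power 0.805.

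Three things do not stand. The composite should not carry the name ORR, because 2.1 and 12.5 give that name to CR+PR and a positive result need contain neither. It should not be set beside the chlorambucil 30%, and the 10% has no stated basis. The decision set is contradictory across 3.2, 14.2, 14.4.1 and 14.4.2. Depending on how that is resolved, the cut-off of 5 gives a type I error between about 0.040 (35 analysed, 29 able to respond, power about 0.72) and 0.082 (35 analysed, all at 10%). The 0.053 to 0.082 range for 30 to 35 patients uses only the plan's 10%, but assumes that every patient counted has that chance. This should be fixed before results are reported.

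**What to change.** - Keep the composite as the tested endpoint at both stages. Name it clinical benefit (biologic response or better) in 2.1, 14.1 and 14.2, including in the final rule.
- Use the 12.4 definition of biologic response throughout, and add it to the categories in 14.4.2.
- Report CR+PR as the ORR, separately, with an exact 95% CI. State that duration of response covers CR and PR only.
- Make no ORR or chlorambucil claim from the composite test. State a basis for 10% and 30% as composite rates, or say that there is none.
- Reconcile 3.2, 3.3, 14.2, 14.4.1 and 14.4.2 into one decision set. Apply the cut-off of 5 to the 29 patients it was derived for, identified by a prespecified rule that fits the evaluability and replacement provisions of 3.3 and does not depend on outcome. Report the all-eligible estimate (up to 35) separately. If the number tested is not 29, state the attained type I error and power.
- Section 10.5 records that accrual closed on 4/12/2016, so date the clarification and say whether outcome data had been seen.

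The cost is wording plus one proportion with its interval from data already collected. Cut-offs, sample size and the stage I rule do not change. The downside is that a positive result supports a more modest claim.

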#### 14.2 Sample Size/Accrual Rate

The sample size is calculated for a single arm, Simon optimal 2-stagephase II deign. The design to test the null hypothesis that  $P \le 0.1$  versus the alternative that  $P \ge 0.3$  has a sample size of 29 and a probability of early termination of 0.74 under the null. The power is 0.8 with statistical significance declared at an alpha level of 0.05. An accrual goal of 35 patients will be enrolled in this study to allow 20% ineligibility or drop outs. According to the Simon 2-stage method, 10 patients will be accrued initially during stage I. If there is evidence of clinical benefit, the remaining 25 patients will be enrolled during stage II. For the purpose of stopping the trial for futility, clinical benefit is defined as biologic response or better (please refer to section 12.4 for the definition of biologic response).

In the planned Simon 2-Stage analysis, 10 patients will be enrolled in stage I. An interim analysis will be performed after the 10th patient completes the induction therapy period. If 1 or fewer patients exhibit clinical benefit (biologic response or better), the trial will be stopped. If 2 or more patients demonstrate clinical benefit, the study will proceed to stage II and an additional 19 patients will be enrolled and treated. If the trial goes on to the second stage, a total of 29 eligible patients will be studied. If the total number responding is less than or equal to 5, the drug combination is considered not worth further exploration. The entire study group of 35 patients will be evaluated in the final analysis.

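### The 29-patient Simon design is calculated correctly, but sections 3.2, 3.3, 14.2 and 14.4.2 conflict on which patients its cut-offs (1 of 10, then 5 of 29) count

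*Combined protocol and SAP*

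**What the plan says.** Section 14.2 tests P of at most 0.1 against P of at least 0.3 with a Simon optimal design of 29 patients, alpha 0.05, power 0.8 and early termination 0.74 under the null. It does not say in which patients P is measured.

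- **Stage I (14.2).** "10 patients will be enrolled in stage I", and "An interim analysis will be performed after the 10th patient completes the induction therapy period". One or fewer with biologic response or better stops the trial.
- **Stage II (14.2).** One paragraph says "the remaining 25 patients will be enrolled during stage II"; the next says "an additional 19 patients will be enrolled and treated".
- **Final rule (14.2).** "If the trial goes on to the second stage, a total of 29 eligible patients will be studied", followed by "If the total number responding is less than or equal to 5, the drug combination is considered not worth further exploration". The next sentence is "The entire study group of 35 patients will be evaluated in the final analysis". There is no cut-off for 35, and that analysis is not called descriptive.
- **Allowance.** The accrual goal of 35 is "to allow 20% ineligibility or drop outs" (14.2). Section 3.2 makes 35 a maximum, meant to yield 29 *evaluable* patients; 14.2 calls the 29 *eligible*.
- **Early leavers.** Section 3.3 and the first sentence of 14.4.2 make a patient with fewer than 2 cycles not evaluable for response, and 3.3 says such patients may be replaced, without limiting this to a stage. The second paragraph of 14.4.2 puts all eligible patients, with the possible exception of the untreated, in the main response analysis and counts categories 4 to 9, including unknown, as failures.

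Section 14.1 plans point estimates and 95% intervals but names no denominator. Section 10.5 records that accrual closed on 4/12/2016.

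**The concern.** *Eligible* and *evaluable* are different sets here: an eligible patient who stops in cycle 1 belongs to the first and not to the second. Under 3.3 that patient can be replaced and does not count. Under the second paragraph of 14.4.2 the same patient is a non-responder in the main analysis. With 29 eligible, 29 evaluable and all 35 named in different places, the same trial data could pass or fail depending on which sentence is followed.

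This is the primary go/no-go rule. Applying 5 to more than 29 assessable patients makes it easier to pass an inactive regimen. Keeping early leavers as failures, above all among the first 10, makes it easier to stop an active one.

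**Working it through.** **Inputs.** From 14.2: p0 = 0.10, p1 = 0.30, n1 = 10, r1 = 1, r = 5, n = 29, and 35 for the final analysis. The 20% loss figure is in 3.2 and 14.2. Leaver rates of 5% and 10% are assumptions; 17% is the implied 6/35.

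**Formulas.** With b(x; m, p) the binomial probability,

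- P(stop at stage I) = b(0; 10, p) + b(1; 10, p)
- P(pass) = Σ over x = 2 to 10 of b(x; 10, p) × P(Y ≥ r + 1 − x), with Y ~ Bin(n − 10, p)

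P(pass) is alpha at p0 and power at p1.

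**Step 1: the plan's own figures.**

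- Early termination at 0.10: 0.3487 + 0.3874 = 0.736 (stated 0.74). At 0.30: 0.0282 + 0.1211 = 0.149.
- Alpha (x = 2, 3, 4, 5, then 6 or more): 0.1937×0.1150 + 0.0574×0.2946 + 0.0112×0.5797 + 0.0015×0.8649 + 0.0001 = 0.047.
- Power: 0.2335×0.8668 + 0.2668×0.9538 + 0.2001×0.9896 + 0.1029×0.9989 + 0.0473 = 0.805.

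A search over all two-stage designs returns 1/10, 5/29 as the Simon optimal one. The design is right.

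**Step 2: other denominators, every patient assessable, stage I cut-off 1/10.**

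| Final rule | Alpha | Power |
|---|---|---|
| 5/28 | 4.2% | 79.3% |
| 5/29 | 4.7% | 80.5% |
| 5/30 | 5.25% | 81.5% |
| 5/35 | 8.2% | 84.0% |
| 6/35 | 3.9% | 81.9% |

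**Step 3: eligible leavers counted as failures in both stages.** Assume 10% and 30% are rates among patients who stay, so a fraction d of leavers gives p(1 − d).

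| d | 5/35 alpha | 5/35 power | 5/29 alpha | 5/29 power |
|---|---|---|---|---|
| 5% | 6.8% | 81.0% | 3.8% | 76.6% |
| 10% | 5.5% | 77.5% | 3.0% | 72.0% |
| 17% (6/35) | 4.0% | 71.5% | 2.1% | 64.4% |
| 20% | 3.5% | 68.8% | 1.8% | 61.0% |

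With 5/35 the loss comes largely from the stage I gate. At a 30% response rate the chance of stopping there rises from 14.9% to 24.7% (d = 17%) or 26.7% (d = 20%). If stage I leavers are replaced and only the 25 stage II patients suffer the 17% to 20% loss, 5/35 has alpha 5.7% to 5.3% and power 81.7% to 81.1%.

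**Step 4: the reverse assumption.** If 10% and 30% are rates among all treated patients, leavers never respond, and they are replaced, the rates among evaluable patients are p/(1 − d): 12.1% and 36.2% at 17%, 12.5% and 37.5% at 20%. Then 5/29 has alpha 9.7% to 11.0% and power 91.4% to 92.8%.

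**Step 5: the allowance.** 29 × 1.2 = 34.8, hence 35. But 35 × 0.8 = 28, and 35 − 29 = 6 is 6/35 = 17%. Also 25 − 19 = 6.

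**The case against.** The best defence is that the intended reading is plain. Section 3.2 makes 35 a ceiling on enrolment to reach 29 evaluable patients. In 14.2 the cut-off of 5 directly follows the 29, and the sentence on 35 comes after the rule with no cut-off of its own. Section 3.3 already allows replacement at either stage. Much of this stands: it is the most natural reading, and it keeps alpha and power as stated. What it does not answer is the second paragraph of 14.4.2, which names all eligible patients as the main response analysis and so gives a different rule for the same early leaver. Replacement in 3.3 is also optional.

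Two stronger conclusions are tempting and are not supported.

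- **That the trial's alpha is 8.2%.** This needs all 35 patients assessable with no loss, whereas 3.2 includes the extra six only to cover losses. It is a ceiling; at 30 patients the excess over 5% is trivial.
- **That power is really about 70%.** This treats the whole 17% to 20% allowance as eligible drop-outs. The plan's 20% covers ineligibility and drop-out together, and the failure rule in 14.4.2 covers only eligible patients. It also takes 10% and 30% as rates among patients who stay. If they are all-eligible rates, leavers are already in P and this loss does not arise.

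The 25-versus-19 difference and the 20% label are minor.

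**Conclusion.** The sample size and both cut-offs are correct; the text on whom they count is wrong as written and should be fixed. The contradiction is in the current text, not in the summary of changes, and its poles are rules that the plan itself states.

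Its size depends on the reading. It is nil under 29 evaluable patients with P defined among them. Otherwise alpha can reach 8.2% (5/35, zero loss). Power can fall to between 81.0% and 68.8% (5/35), or between 76.6% and 61.0% (5/29), for 5% to 20% eligible leavers counted as failures in both stages, if P describes patients who stay. Apart from the plan's combined 20%, these leaver rates are assumptions.

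A reader might infer that the design was miscalculated, or that the population was left open so as to be chosen after seeing results. The first is disproved by the reproduction. On the second the documents are silent: they do not say whether responder counts were known when the current version was dated.

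**What to change.** In 14.2, name one decision population for both cut-offs and say that P refers to it. Either:

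- **(a)** use the first 10 and first 29 evaluable patients in enrolment order, with cut-offs 1 and 5, P defined among evaluable patients, and the 35-patient analysis called descriptive; or
- **(b)** if all 35 eligible patients decide, keep 1/10 and use 6 or fewer at the end (alpha 3.9%, power 81.9%, with P an all-eligible rate).

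Reconcile 3.3 with both paragraphs of 14.4.2 so that one early-leaver rule governs the decision, and report the result under the other rule too. This is a choice between two stated rules, so record it as a choice and not only as a clarification. Use one word, *evaluable* or *eligible*, in 3.2 and 14.2. Say that 25 is 19 plus the allowance of 6, if that is meant, and restate the allowance as 17%.

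Because accrual has closed, date the change and make it without reference to responder counts. If the counts are already known, report the decision under both denominators.

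The cost is text in 3.2, 3.3, 14.2 and 14.4.2 and a dated note; no extra patients. Option (a) has a price: later patients do not enter the decision, and if 10% and 30% were meant as all-treated rates, dropping leavers inflates alpha to 9.7% to 11.0% (Step 4). It raises power in that case; it does not lower it.
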